6.1 Inclusion Criteria

Subjects must be \geq 18 years of age and have had an RT-PCR test performed prior to enrollment. Subjects must be able to understand and willingly sign a written informed consent. Additionally, participants need to meet at least 1 of the criteria listed below:

- Currently experiencing symptoms of COVID-19.
- Be clinically diagnosed or suspected to have COVID-19.
- Recent past (3 weeks) exhibited symptoms of COVID-19.
- Be capable of performing a self-collection of a nasopharyngeal sample with use of nasal swab kit.
- Interacted with a COVID-19 positive individual.

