Subjects must meet inclusion and exclusion criteria.

Investigational

Product: BIOZEK COVID-19 Antigen Rapid Test Cassette (Nasopharyngeal Swab)

Comparator: Type of test: **RT-PCR**

Name of test: Lyra Direct SARS-CoV-2 Assay

Manufacturer: Quidel Corporation

Study Design: Up to 250 symptomatic subjects of age 18 or older that meet the inclusion

and exclusion criteria and are willing to participate will be enrolled into the BIOZEK study. All subjects will be required to sign an informed

consent form.

Participants will complete a personal information form and a testing site personnel will collect medical history and vital signs will be recorded.

2

Medical clearance will be obtained prior to performing any sample collection.

Subject will have 3 tests performed in a manner described below:

1.RT-PCR test (by medical staff prior to enrollment as a standard of care procedure), Additionally Ct value will be requested. Turnaround time for RT-PCR test results is 1-2 days.

2.BIOZEK COVID-19 Antigen Rapid Test (via self-collection),

Nasopharyngeal samples will be collected via self-collection and the test will be performed by the subject. The participants will follow instructions for use provided by Biozek together with the test. The subject's performance during self-collection and test performance will be monitored and recorded in a performance form. Results in 15 minutes.

3. BIOZEK COVID-19 Antigen Rapid Test (by medical staff).

Second, a nasopharyngeal sample will be collected and a test will be performed by a medical professional. Results for the test in 15 minutes. A coordinator will monitor patient concerns during and after collection and an image will be captured of the results of both tests for record and in subject's CRF. Compliant to all procedures for disposal of biohazardous waste.

Results will be retrieved from the PCR test when available and all three samples will be analyzed and compared.

Criteria for Evaluation:

During self-collection the subject will be closely monitored according to **Safety Criteria:**

> standard of care and any adverse effects will be captured. During the test performed by a healthcare professional, the subjects in this study will not be exposed to additional risk from interventional procedures, because the

ones to be used are the standard of clinical practice.

Efficacy Criteria: Sensitivity and Specificity will be calculated separately for BIOZEK

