6.2 Exclusion Criteria

Subjects who meet any of the following exclusion criteria may not be enrolled in this study:

- Cannot perform self-collection of a nasopharyngeal sample with use of nasal swab kit.
- Have a deviated nasal septum.
- Cognitively impaired individuals resulting in the inability to provide informed consent

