7.2 Material and Methods

Enrollment will take place at the Mobile Clinic. The Enrollment population consists of up to 250 symptomatic patients scheduled for an appointment, at a Mobile Clinic, to perform an RT-PCR test for SARS-CoV-2 as the standard of care procedure. After arrival, all patients who have received an RT-PCR test will complete a COVID Screening Intake Form and will be asked if they are willing to participate in the BIOZEK study after their scheduled RT-PCR test has been performed. After obtaining medical clearance, a medical staff member will collect samples for RT-PCR test and will send it to the Sigmund Laboratory for testing. The results will be available in 1-2days. Results and Ct value of the RT-PCR test from subjects enrolled to the study will be collected by study personnel.

If the subject is age 18 or older and meets the inclusion and exclusion criteria, they will sign an Informed Consent Form and will be enrolled into the BIOZEK study. A study coordinator will take the subject's body's surface temperature and will capture it in the CRF.

An additional two samples will be collected for the BIOZEK COVID-19 Antigen Rapid Test. The first test will be performed by the subject, via self-collection of the sample, following instructions provided by Biozek Company. The second test will be performed by a trained medical professional.

Subject will open the Biozek package with a test and will read instructions in package insert. Materials provided in the BIOZEK-COVID-19 Antigen Rapid Test kit includes: Test cassettes, Sterile Swabs, Extraction tubes and tips, Extraction Buffer, Workstation.

First sample collection- BIOZEK COVID-19 Antigen Rapid Test

[figure not shown]
A nasopharyngeal sample will be collected via self-collection and the test will be performed by the subject. The subject will follow simplified instruction provided with the test. (Instructions listed below and the full instruction is also attached). Medical professionals will monitor and record any difficulties.

BIOZEK COVID-19 Rapid Test

DIRECTIONS

Read all of these directions before starting

- 1. Open the swab package.
- 2. Twist top off the small plastic vial and squeeze the liquid into the plastic specimen tube, making sure the specimen tube stays upright.
- 3. Collect the specimen from your nose.

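### Ability to self-collect is one of the alternative inclusion criteria, so the symptom and exposure items screen out nobody and the stated symptomatic population is not enforced

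*Combined protocol and SAP*

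**What the plan says.** Section 6.1 first requires age 18 or over, a prior RT-PCR test and written consent. It then adds: "Additionally, participants need to meet at least 1 of the criteria listed below". Five items follow: current symptoms, clinical diagnosis or suspicion, "Recent past (3 weeks) exhibited symptoms of COVID-19", contact with a positive individual, and "Be capable of performing a self-collection of a nasopharyngeal sample with use of nasal swab kit".

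Section 6.2 excludes anyone who meets this description: "Cannot perform self-collection of a nasopharyngeal sample with use of nasal swab kit". Its other two exclusions are a deviated septum and cognitive impairment that prevents consent.

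The population is described in three other places:

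- Synopsis, Study Design: "Up to 250 symptomatic subjects of age 18 or older that meet the inclusion" and exclusion criteria.
- Section 7.2: "The Enrollment population consists of up to 250 symptomatic patients scheduled for an appointment".
- Synopsis, Target Population: adults who want an RT-PCR test, subject to the inclusion and exclusion criteria. Symptoms are not mentioned.

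On the enrolment procedure, section 7.2 says that "all patients who have received an RT-PCR test will complete a COVID Screening Intake Form and will be asked" whether they will take part, and then: "If the subject is age 18 or older and meets the inclusion and exclusion criteria, they will sign an Informed Consent Form".

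**The concern.** A criterion that everyone must meet has been placed in a list where meeting any single item is enough. That cancels the other items. The result is a set of criteria that does not select for symptoms, beside two descriptions of the population that say it is symptomatic.

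The primary endpoint is sensitivity and specificity, and both are properties of a test in a particular population. The Introduction (section 2) says rapid tests work best early in infection, when viral load is high, so the mix of subjects can move the sensitivity estimate. Section 8 plans no analysis by symptom status. The Ct analysis announced in section 4 bears on viral load among RT-PCR positives. It says nothing about specificity or about who was enrolled.

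There is also a consequence for conduct. Section 7.4 treats enrolment of an ineligible patient as a major violation, and any other departure from the protocol as a violation to be reported at once. A subject without symptoms satisfies 6.1 and 6.2 but departs from the description in 7.2, so the site cannot tell whether that enrolment is reportable.

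**Working it through.** The plan states no figure on this point to reproduce. The check is of the eligibility logic, followed by a precision calculation that bears on the fix.

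**Step 1: the criteria as written.** Let C = current symptoms, D = diagnosed or suspected, P = symptoms in the past three weeks, E = exposure, S = able to self-collect.

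- Section 6.1 list: C or D or P or E or S.
- Section 6.2, first exclusion: not S. Passing 6.2 therefore implies S.
- S alone makes the 6.1 list true, so passing 6.2 implies passing the list, whatever C, D, P and E are.

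Take age, prior RT-PCR and consent as met. Among those who pass 6.2, the four remaining items give 2⁴ = 16 yes/no profiles:

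| Rule | Admitted | Of these, no current symptoms | Neither current nor recent symptoms | None of C, D, P, E |
|---|---|---|---|---|
| As written | 16 of 16 | 2³ = 8 | 2² = 4 | 1 |
| S taken out of the list, at least one of C, D, P, E | 15 of 16 | 8 − 1 = 7 | 4 − 1 = 3 | 0 |
| S taken out of the list, C required | 2³ = 8 of 16 | 0 | 0 | 0 |

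These are logical profiles, not shares of patients.

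**Step 2: is removing S enough?** No. Of the four remaining routes, three (D, P, E) do not require current symptoms, and two (D, E) require neither current nor recent symptoms. Moving the self-collection item restores some selection but does not make the population symptomatic.

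**Step 3: does another step impose symptoms?** Section 7.1 has staff screen subjects and judge them eligible, but names no symptom check. Section 7.2 invites the patients who have had the RT-PCR test, then checks age and the criteria. No stated step makes symptoms a condition of entry.

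**Step 4: precision if results are split by symptom status.** Section 6.3 sets minimums of 30 positive and 30 negative results. Assume these are RT-PCR results, that half of each fall in each subgroup, and, for illustration, the observed counts below. The exact (Clopper-Pearson) 95% limits for x out of n are the 0.025 quantile of Beta(x, n − x + 1) and the 0.975 quantile of Beta(x + 1, n − x).

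| Measure | Overall | One subgroup |
|---|---|---|
| Sensitivity, 80% observed | 24/30: 61% to 92% | 12/15: 52% to 96% |
| Specificity | 29/30: 83% to 99.9% | 14/15: 68% to 99.8% |

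At the minimum sample, the sensitivity interval widens from 30.9 to 43.8 percentage points and the specificity interval from 17.1 to 31.8.

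**The case against.** The strongest reply is that the word symptomatic is itself a restriction. The Synopsis wording joins it to the criteria, and section 7.2 opens by defining the pool as symptomatic patients with appointments, so those later invited could be read as members of that pool. An intake form is completed and a medical history taken, and these may capture symptoms; the forms are not in the documents. This reading is available, but it does not remove the conflict. Section 6.1 accepts exposure alone or past symptoms alone as sufficient, which would serve little purpose if everyone had to be symptomatic, and no stated enrolment step applies the restriction.

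A second reply is that a broad population was intended. The Target Population entry is broad, and the Introduction sees promise in antigen tests for screening people without symptoms. On that view the error is mainly the word symptomatic. That may be so, and it is why the choice belongs to the sponsor. The self-collection item would still be misplaced.

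Third, the harm is not quantified. This stands: the Introduction links performance to stage of infection rather than to current symptoms, so neither the direction nor the size of an effect can be derived. Three smaller points also stand. The reporting problem under section 7.4 follows from the same ambiguity and is not separate evidence. Exposure is not strictly a clinical state. Reporting by symptom status is an addition that no stated objective requires.

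**Conclusion.** The concern holds and must be fixed. As written, none of the four symptom, diagnosis or exposure items can reject anyone who passes section 6.2, and the symptomatic population named in the Synopsis and section 7.2 is not enforced by the criteria. This follows from the wording alone. It does not mean that entry is unrestricted: age, prior RT-PCR, consent and the section 6.2 exclusions still apply.

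The count of three routes that bypass current symptoms matters only if symptomatic means currently symptomatic, which the documents do not define. The effect on sensitivity and specificity is unknown, because the documents give neither the patient mix nor performance by symptom status. The rule is wrong as written rather than merely short on detail: a site that follows it exactly can enrol people outside the stated population. The Target Population entry defers to the criteria and only needs aligning.

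**What to change.** 1. Take the self-collection item out of the list of alternatives in section 6.1. Section 6.2 already covers it.
2. Decide on one intended population, reconcile the Synopsis (Study Design), 6.1 and 7.2 on it, and align the Target Population entry.
   - *If symptomatic:* make symptoms a required criterion and state whether symptoms in the past three weeks count.
   - *If mixed:* keep the requirement for at least one of the four remaining items and replace the word symptomatic in the Synopsis and 7.2 with the groups actually admitted. Record which items each subject met. Preferably add to section 8 that sensitivity and specificity are reported by current-symptom status as well as overall, alongside the Ct analysis.

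The cost is a wording amendment, which section 9.1 makes subject to IRB approval, plus one sentence in section 8 if the population is mixed. A new CRF field is needed only if the existing forms do not already capture the items. There are two downsides. People with none of the four items become ineligible. Subgroup estimates at the minimum sample are too imprecise for anything but description.

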6.2 Exclusion Criteria

Subjects who meet any of the following exclusion criteria may not be enrolled in this study:

- Cannot perform self-collection of a nasopharyngeal sample with use of nasal swab kit.
- Have a deviated nasal septum.
- Cognitively impaired individuals resulting in the inability to provide informed consent

6.3 Sample Size

Up to 250 subjects will be enrolled in the study. The study shall be continued until at least 30 positive and 30 negative tests results are obtained.

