Clinical Protocol BIOZEK

Title: "Open label, Single-Center Study utilizing BIOZEK COVID-19

Antigen Rapid Test as compared to standard testing technique." Test performed by a professional versus self-collection and standard

of care.

Short title: Comparison of BIOZEK Antigen Rapid Test to

COVID-19 RT-PCR.

Protocol Number: Biozek-ARTC-US/001/3-5-2021

Product: BIOZEK COVID-19 Antigen Rapid Test Cassette

(Nasopharyngeal Swab)

Contract Research Organization (CRO): [name], PhD

Principal Investigator: [name]. **Co-Principal Investigator**: [name]

Study Management

and Monitoring: [name]

Study Coordinator: [name]

Version: Final 1.0

Date: March 5, 2021

CONFIDENTIALITY STATEMENT

The information contained in this document, particularly unpublished data, is the property or under control of Biozek medical and is provided to you in confidence as an investigator, potential investigator, or consultant, for review by you, your staff, and an applicable Institutional Review Board or Independent Ethics Committee. The information is only to be used by you in connection with authorized clinical studies of the investigational drug described in the protocol. You will not disclose any of the information to others without written authorization from Biozek Company, except to the extent necessary to obtain informed consent from those persons to whom the test may be performed.

1. Protocol Synopsis

Title: "Open label, Single-Center Study utilizing BIOZEK COVID-19

Antigen Rapid Test as compared to standard testing technique." Test

performed by a professional vs self-collection and standard of care.

Study Site

Sample Collection: Mobile Covid Services LLC

[name]

[name]

Sigmund Laboratory for RT-PCR test

[name]

[name]

Number of Subjects

Planned: Up to 250 Subjects, minimum of 30 positive and 30 negative tests.

Study Objectives: Primary:

To assess sensitivity and specificity of BIOZEK COVID-19 Antigen

Rapid Test on a sample collected by a healthcare professional.

Secondary:

To assess sensitivity and specificity of BIOZEK COVID-19 Antigen

Rapid Test on a self-collected sample.

To assess if the result of each BIOZEK COVID – 19 Antigen Rapid Test

performed by the subject are the same as the results of the test performed

by a healthcare professional.

Target Population: Subjects, at least 18 years of age who desire a Covid-19 RT-PCR test.

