 - a. Gently insert the swab into your nose, all the way to the back of the nasal cavity. (NOTE: Aim the swab towards the back of your head, not towards the top, as your nasal cavity connects back to your ears)
 - a. When the swab can't be pushed any further (inserted about 3") rotate it 3 times and gently and carefully remove the swab.
- 4. Insert the swab into the specimen tube.
 - a. Rotate the swab for 10 seconds against the wall of the tube.
 - b. Squeeze the bottom of the tube several times while stirring.
- 5. Remove the swab while squeezing the tube to get the maximum solution out of the swab.
- 6. Place the plastic tip on the specimen tube.
- 7. Open the test cassette and place it on a level surface.
- 8. Shake the specimen tube for 10 seconds.
- 9. Invert the specimen tube and put 3 drops into the specimen well of the cassette test kit.
- 10. Wait for 15 minutes and read the results.

After interpreting the results, the coordinator will take an image of the cassette to be recorded and captured in the CRF. Compliant to all procedures required for disposal of biohazardous waste.

Second sample collection- BIOZEK COVID-19 Antigen Rapid Test

A nasopharyngeal sample collection and the test will be performed by a medical professional. The medical professional is trained and will not require instructions to perform the test. After specimen collection, the coordinator records any indication of an adverse event and it is captured in the CRF. All data collected is to be captured in the subject's CRF.

The swab specimens should be extracted and tested as soon as possible after specimen collection. After interpreting the results, the coordinator will take an image of the cassette to be recorded and captured in the CRF. Compliant to all procedures required for disposal of biohazardous waste.

RT-PCR test collection and processing will follow the standard of care procedure. In addition, Ct values will be requested from the laboratory. Turnaround time for RT-PCR test results is 1-2 days. When the results from PCR test will be available study personnel will collect them from Sigmund Laboratory. All three results will be compared.

All data collected from the three samples will be transferred to Quality Research and Invention, LLC for analysis.

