7.6 Risks

During self-collection the subject will be closely monitored according to standard of care and any adverse effects will be documented. During the test performed by healthcare professionals the subjects in this study will not be exposed to additional risk from interventional procedures, because the ones to be used are the standard of clinical practice.

8. Data analysis

The data will be collected and analyzed by Quality and Invention team.

Results of RT-PCR, BIOZEK COVID-19 Antigen Rapid Test on a sample collected by healthcare professionals, BIOZEK COVID-19 Antigen Rapid Test on self-collected samples will be analyzed. Additionally, Ct values for RT-PCR will be obtained.

RT-PCR is a golden standard in diagnosis of Covid-19. The results obtained by Biozek tests will be compared to results of RT-PCR test.

Sensitivity and specificity will be calculated.

9. Ethics

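### Does the 30-positive, 30-negative enrolment rule in Section 6.3 need to name the test it counts and say what happens at 250 subjects?

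*Combined protocol and SAP*

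**What the plan says.** The Synopsis gives the planned number as "Up to 250 Subjects, minimum of 30 positive and 30 negative tests". Section 6.3 repeats it in two sentences: "Up to 250 subjects will be enrolled in the study", then "The study shall be continued until at least 30 positive and 30 negative tests results are obtained". Neither place names the test being counted.

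The Study Design part of the Synopsis says "Subject will have 3 tests performed in a manner described below", and lists RT-PCR, a self-performed BIOZEK test and a professionally performed BIOZEK test. Section 7.2 adds that "Turnaround time for RT-PCR test results is 1-2 days", while a BIOZEK result is read on site at 15 minutes.

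Section 8 (Data analysis) calls RT-PCR the gold standard and says "The results obtained by Biozek tests will be compared to results of RT-PCR test". On the statistics it says only "Sensitivity and specificity will be calculated".

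No expected positivity, target precision, power or acceptance threshold appears anywhere.

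**The concern.** With three results per subject, a count of test results can be read in more than one way. It could mean RT-PCR-positive subjects, positive professional BIOZEK results, or results pooled across tests. The readings guarantee different numbers of RT-PCR positives, and that number is the denominator of sensitivity, which is half of the primary endpoint. BIOZEK results are available days before RT-PCR results, so a tally kept on site is conceivable.

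The two sentences of Section 6.3 can also collide. If the 250th subject has been enrolled and fewer than 30 RT-PCR positives have been found, continuing breaches the cap and stopping breaches the continuation rule. The sections on withdrawal, replacement and discontinuation do not cover this case.

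Section 8 plans no confidence interval, so a small denominator might not be visible beside the estimate. At stake is the precision of sensitivity. Specificity is not threatened.

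**Working it through.** **The plan's own figures.** The 250 and the 30/30 cannot be reproduced, because the protocol gives no formula, prevalence or precision behind them. The checks below therefore ask what follows from them.

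**Which unit is meant.** Four statements bear on this:
- The primary endpoint is sensitivity and specificity of the professionally collected BIOZEK test.
- Sensitivity is the number positive on both BIOZEK and RT-PCR, divided by the number positive on RT-PCR. Specificity is the same with negatives.
- Section 8 names RT-PCR as the comparator.
- The rule asks for minimum numbers of both positives and negatives.

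Minimum numbers of positives and negatives are what fix the two denominators, and those denominators are RT-PCR-positive and RT-PCR-negative subjects. No sentence suggests adding up results across a subject's tests. Pooling would indeed give a small guarantee: 30/2 = 15 subjects positive on both BIOZEK tests, or 30/3 = 10 positive on all three. But nothing in the protocol leads an analyst there.

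**The one plausible alternative: counting professional BIOZEK results.** Assumed: sensitivity 80%, specificity 98%, cap 250, stopping at 30 positive and 30 negative professional BIOZEK results (20,000 simulated trials). Mean RT-PCR positives at stopping are 32.1, 34.1 and 35.4 at positivity 15%, 20% and 30%. The share of trials ending with fewer than 30 is about 21%, 7% and 2%. At 15% positivity the cap alone accounts for about 7.5 of those 21 percentage points (1 − 0.925, next table).

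**The cap, counting RT-PCR positives.** Inputs: 250 and 30 from Section 6.3; positivity *p* assumed. With X ~ Binomial(250, *p*), the expected number of positives is 250*p* and the chance of meeting the minimum is P(X ≥ 30).

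| Assumed positivity | Expected positives | P(X ≥ 30) |
|---|---|---|
| 8% | 20 | 0.02 |
| 10% | 25 | 0.17 |
| 12% | 30 | 0.53 |
| 15% | 37.5 | 0.93 |
| 20% | 50 | above 0.99 |

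A 90% chance needs positivity of about 14.6%. For negatives, P(at least 30 in 250) exceeds 0.999 at every positivity from 5% to 30%.

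**What a shortfall costs.** Exact (Clopper-Pearson) 95% intervals at an observed sensitivity of 80%:

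| Result | Interval | Width |
|---|---|---|
| 24/30 | 61% to 92% | 31 points |
| 20/25 | 59% to 93% | 34 points |
| 16/20 | 56% to 94% | 38 points |

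Falling from 30 to 20 positives lowers the lower bound by 61 − 56 = 5 points.

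**Results pending when the target is met.** The rule says at least 30, so overshoot is allowed. Section 7.2 has RT-PCR results collected when they arrive, all three results compared, and all data sent for analysis. Subjects enrolled during the 1-2 day wait are therefore included.

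**The case for a change.** The best case for a change is that both gaps are real on the text and cheap to close. A few words in Section 6.3 and the Synopsis would name RT-PCR status as the unit and say that the cap governs. Low positivity cannot be ruled out either. Section 7.2 describes "The Enrollment population consists of up to 250 symptomatic patients scheduled for an appointment", but Section 6.1 requires only one item from a list that includes contact with a positive individual, symptoms within the past three weeks, or simply being able to self-collect. At 10% positivity, 250 subjects would miss 30 positives with probability 1 − 0.17 = 0.83. Counting BIOZEK results on site is not wholly harmless: at 15% positivity about one simulated trial in five ends below 30 RT-PCR positives, which a mean of 32 conceals.

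All of this stands as description. Neither statement of the rule names its unit, and no text deals with a shortfall. It does not show that the plan, followed on its natural reading, gives a wrong answer. The estimates are valid at whatever denominator is reached. A shortfall widens an interval that is already wide at 30, and the plan ties no decision to a particular width. Adding more than 250 subjects would be a different study size, which nobody proposes. A statement that the cap governs would record what up to already conveys.

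The missing confidence intervals are a reporting detail. An analyst presenting sensitivity would ordinarily give the numerator, denominator and an exact or Wilson interval, and the planned data are enough to compute them.

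**Conclusion.** No change follows. The rule leaves two details unwritten, and ordinary reading fills both: the count is of RT-PCR-positive and RT-PCR-negative subjects, and enrolment ends at the target or at 250, whichever comes first.

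Under that reading a shortfall in positives is a real possibility only if positivity is below about 15%, a figure the protocol does not give and which is assumed here across a range. If it happened, the loss would be modest: about 5 points on the lower confidence bound in going from 30 positives to 20, at an assumed observed sensitivity of 80%. Specificity is unaffected. No stated power, hypothesis or threshold would be missed.

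The conclusion rests on analysts using RT-PCR status as the denominator, as Section 8 implies, and on results being presented with their denominators. It would be different if there were any sign that results were to be pooled across a subject's tests, or if the plan had set a precision or performance threshold that depends on 30 positives. The protocol contains neither.
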